### 15.1.1 Primary Analysis of Primary Efficacy Endpoint

The primary objective of the study will be evaluated for SHR0302 dose groups (8mg QD, 4mg BD, 4mg QD) compared to placebo group with respect to the percentage of patients with clinical response at week 8. The aim of the study is to detect at least 1 dose group different from placebo group by using Hochberg's step up test. The primary analysis will be based on the FAS population.

Hochberg's step-up method for multiple testing was developed in 1988 to control the familywise error rate. The familywise error rate is the probability of coming to at least one false conclusion in a series of hypothesis tests. In other words, it's the probability of making at least one Type I Error. Hochberg's method is thought of as a step-up version of the Bonferroni test.

The Hochberg method will be used to maintain the 2-sided study-wise Type I error rate at 0.1. The null and alternative hypothesis for the primary endpoint that will be tested are:

- $H_{01}$ : The percentage of patients with clinical response at week 8 in SHR0302 8mg group – the percentage of patients with clinical response at week 8 in placebo group = 0;
- $H_{11}$ : The percentage of patients with clinical response at week 8 in SHR0302 8mg group – the percentage of patients with clinical response at week 8 in placebo group  $\neq$  0.
- $H_{02}$ : The percentage of patients with clinical response at week 8 in SHR0302 4mg BD group – the percentage of patients with clinical response at week 8 in placebo group =

0;

- $H_{12}$ : The percentage of patients with clinical response at week 8 in SHR0302 4mg BD group – the percentage of patients with clinical response at week 8 in placebo group  $\neq$  0.
- $H_{03}$ : The percentage of patients with clinical response at week 8 in SHR0302 4mg QD group – the percentage of patients with clinical response at week 8 in placebo group = 0;
- $H_{13}$ : The percentage of patients with clinical response at week 8 in SHR0302 4mg QD group – the percentage of patients with clinical response at week 8 in placebo group  $\neq$  0.

[figure not shown]

Figure 2. The decision rules of hypothesis

For clinical response at week 8, the comparisons of the percentage of patients achieving clinical response in each treatment versus placebo will be made using a stratified Cochran-Mantel-Haenszel (CMH) test with stratification according to prior anti-TNF $\alpha$ /biological treatment (with or without). The CMH method is a technique that generates an estimate after adjusting for or taking into account stratification. Strata-adjusted proportion difference between each SHR0302 dose group and placebo group will be obtained by CMH method [1].

Missing data will be imputed as NCF. If a patient is missing one or more Mayo subscores at the visit where the endpoint is being assessed, the patient would be considered a treatment failure.

Two-sided p-values for the treatment group differences will be provided for all comparisons. Thus, 3 p-values will be gained. Order the three p values as  $(p_{(3)}, p_{(2)}, p_{(1)})$ , where  $p_{(3)} \geq p_{(2)} \geq p_{(1)}$ . The decision rules are provided in Figure 2. Note that in Figure 2,  $H_{(01)}$  is the

corresponding null hypothesis of the smallest p value  $p_{(1)}$ ,  $H_{(02)}$  is the corresponding null hypothesis of the second smallest p value  $p_{(2)}$ , and  $H_{(03)}$  is the corresponding null hypothesis of the largest p value  $p_{(3)}$ . Therefore,  $H_{(01)}$  and  $H_{01}$  may not be the same null hypothesis,  $H_{(02)}$  and  $H_{02}$  may not be the same null hypothesis,  $H_{(03)}$  and  $H_{03}$  may not be the same null hypothesis, either.

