## 3.3 CHANGES TO ANALYSIS FROM PROTOCOL

- Two new analysis sets which are all patients enrolled set and all patients randomized set have been added in this SAP. The reason for these changes is to summarize patient disposition clearly.
- In protocol, per protocol set is defined as all patients from FAS who do not have significant protocol violation. Based on the data before the interim database lock, there are some subjects who do not have primary efficacy results at week 8. In order to assess the primary efficacy results based on observed results without non-completers considered failure (NCF) imputation, these subjects without week 8 efficacy results will be excluded from PP set.

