## 5.4 PER PROTOCOL ANALYSIS SET [PPS]

Per protocol set is defined as all patients from FAS who have week 8 efficacy data and do not have significant protocol violation.

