## 15. EFFICACY ENDPOINTS

### 15.1 PRIMARY ENDPOINT

Mayo score is an instrument designed to measure disease activity of ulcerative colitis. Mayo score ranges from 0 to 12 points. It consists of 4 subscores, each graded from 0 to 3 with higher scores indicating more severe disease. The four subscores are listed below.

- Stool frequency (0-3)
- Rectal bleeding (0-3)
- Findings of colonoscopy (0-3)
- Physician global assessment (0-3)

The Physician global assessment (PGA) is a clinician-reported assessment that reflects "the patient's recorded symptoms, the proctoscopic appearance of the rectosigmoid mucosa, and

Document: \\ieedc-vnasc01\Biosdata\Reistone\SHR0302\CZA55021\Biostatistics

Author: [REDACTED]

Version Number:

Final v1.2

Version Date:

23Mar2021

Template No: CS\_TP\_BS016 Revision 5  
Effective Date: 01Apr2018

Reference: CS\_WI\_BS005

other pertinent clinical indexes, such as physical findings and the patient's performance status.

9-point modified Mayo score is the Mayo score excluding PGA subscore, hence the maximum is 9 points and minimum 0 point. By removing the PGA, it removes the subjective view/assessment from the physicians hence reducing bias. It is also a recommended assessment by the regulators. 9-point modified Mayo score will be collected as a primary endpoint at week 8.

The primary endpoint is the percentage of patient achieving clinical response at week 8 which is defined as decrease from baseline in 9-point modified Mayo score of at least 2 points and at least 30%, with an accompanying decrease in the subscore for rectal bleeding of at least 1 point or absolute subscore for rectal bleeding of 0 or 1.

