### 15.1.2 Sensitivity Analysis of Primary Efficacy Endpoint

Sensitivity analyses for the primary endpoint include:

- Sensitivity to analysis set  
The same analysis will use the per-protocol analysis set
- Sensitivity to missing data assumptions  
The same analysis will use LOCF imputation for subscore other than endoscopy of Mayo score. For missing endoscopy subscore, BOCF imputation will be used .

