## Continuous Secondary Efficacy Endpoints

Change from baseline in 9 point modified Mayo score or total Mayo score at Week 8 will be summarized in each treatment group and overall. Descriptive statistics will be presented. An analysis of covariance (ANCOVA) model will be used to evaluate whether the means of change from baseline are equal across treatment groups, while statistically controlling for the effects of baseline value and previous exposure to anti-TNF $\alpha$  treatment/other biological treatments. The model will include treatment group, baseline value, with/without previous exposure to anti-TNF $\alpha$  treatment/biological treatment as main effects. Least square mean (LS Mean) and 90% CI for each treatment group will be provided at Week 8.

---

Document:

\\\ieedc-vnasc01\Biosdata\Reistone\SHR0302\CZA55021\Biostatistics

Author:

[REDACTED]

Version Number:

Final v1.2

Version Date:

23Mar2021

[figure not shown]
Template No: CS\_TP\_BS016 Revision 5  
Effective Date: 01Apr2018

Reference: CS\_WI\_BS005

A partial Mayo score is the Mayo score without endoscopy component. Hence the maximum is 9 points and minimum 0 point. A partial Mayo score will be assessed at baseline, Week 1, Week 4, Week 8, Week 9, Week 12, Week 16, Week 18, early withdrawal visit and follow up visit, as secondary endpoints.

Changes from baseline in partial Mayo score at Weeks 1, 4, 8, 9, 12 and 16 will be summarized descriptively. For each visit, the change from baseline in partial Mayo score will be calculated. For the change from baseline value at each visit, ANCOVA model including treatment group, baseline value, with/without previous exposure to anti-TNF $\alpha$  treatment as main effects will be used to assess the treatment effect in partial Mayo score. LS Mean and 90% CI for each treatment group will be provided at Week 1, 4, and 8.

A figure will be used to present mean and 90% CI of the partial Mayo score at each visit in each treatment group.

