### 15.2.2 Missing Data for Secondary Efficacy Endpoints

For dichotomized endpoints, missing data will be imputed as non-completers considered failure; if a patient is missing one or more Mayo subscores at the visit where the endpoint is being assessed, the patient would be considered a treatment failure.

For continuous endpoints, missing data will be imputed by using LOCF approach for results other than endoscopy of Mayo score. For missing endoscopy subscore, BOCF approach will be used.

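### A response reached at Week 8 after prohibited or escalated UC therapy can count as a response, while the same breach is a failure if the patient is withdrawn before Visit 5 is complete

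*SAP*

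**What the plan says.** **Endpoint.** SAP 15.1 requires a "decrease from baseline in 9-point modified Mayo score of at least 2 points and at least 30" per cent, together with a rectal-bleeding condition. Medication does not enter the definition, and protocol 1.4.1 and 7.2.1 agree.

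**Failure rules.** SAP 15.1.1 states "Missing data will be imputed as NCF. If a patient is missing one or more Mayo subscores" at the visit in question, the patient is a failure. For the binary secondary endpoints SAP 15.2.2 repeats this: "For dichotomized endpoints, missing data will be imputed as non-completers considered failure", with the same missing-subscore clause. Protocol 9.3.4.2 lists NCF under missing data only. The continuous endpoints follow the same pattern: "For continuous endpoints, missing data will be imputed by using LOCF approach for results other than endoscopy of Mayo score", with BOCF for a missing endoscopy subscore.

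**Therapy rules.** Protocol 6.6.2 bars immunosuppressants, biologics, intravenous and rectal steroids, rectal 5-ASA and other JAK inhibitors. Protocol 6.6.3 bars traditional or herbal UC medicines. Protocol 6.6.1 requires oral 5-ASA/sulfasalazine to be stable and oral steroids to be neither started nor changed up to Week 8, apart from documented reductions for intolerance or safety. None of these sections gives a breach a consequence for response.

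**Withdrawal.** Protocol 5.6 leaves withdrawal to the discretion of the investigator or sponsor. Protocol 5.8 defines early withdrawal as leaving before Visit 5 procedures are finished. Protocol 5.9 requires discontinuation for non-adherence only where staying in is an unacceptable health risk.

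**Sensitivity analyses.** SAP 15.1.2 says "The same analysis will use the per-protocol analysis set", which SAP 5.4 defines as "all patients from FAS who have week 8 efficacy data and do not have significant protocol violation". The other sensitivity analysis changes only how missing scores are filled.

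**The concern.** The primary objective is to compare each SHR0302 regimen with placebo in inducing clinical response. If a patient improves after, say, a rectal steroid or a raised oral steroid dose, the plan as written can credit that improvement to the randomised arm. Two patients with the same breach can also be classified differently because one was withdrawn and the other was not. The plan therefore follows neither a consistent as-observed strategy nor a consistent failure strategy for added therapy.

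If the question is the effect of the drug without added UC therapy, this can bias the drug–placebo difference. More such responders on placebo would shrink it, equal numbers would leave it unchanged, and more on active drug would enlarge it.

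**Working it through.** **Step 1: trace one patient through the rules.** Take a patient who starts a barred UC therapy at Week 5.

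| Course | Rule that applies | Result |
|---|---|---|
| Withdrawn at discretion before Visit 5 is complete | Protocol 5.6 and 5.8; NCF in SAP 15.1.1 | Failure |
| Stays in, a Week 8 subscore is missing | SAP 15.1.1 | Failure |
| Stays in, scores complete, response criteria not met | SAP 15.1 | Non-responder on observed scores |
| Stays in, scores complete, response criteria met | SAP 15.1 | Responder |

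The last row is the gap. SAP 9 lists and summarises deviations and SAP 12 tabulates concomitant medication by arm, but neither is linked to response.

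**Step 2: reproduce the planned power.** Inputs from protocol 9.2.1 and SAP 3.1: response rates of 57%, 57%, 50% and 30% (placebo), 35 evaluable per arm, Hochberg at two-sided 0.10, power for at least one dose. I enumerated all binomial outcomes with a shared placebo arm, using a single-stratum CMH test. With x active responders, m responders in both arms together, n = 35 and N = 70:

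Q = (x − m/2)² ÷ [n²·m(N − m) / (N²(N − 1))], referred to chi-square with 1 df.

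At least one rejection occurs if the largest p ≤ 0.10, or the middle p ≤ 0.05, or the smallest p ≤ 0.0333. Result: **80.1%**, against the stated 80%.

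**Step 3: size of one patient.** 1/35 = 2.9 points. If all 152 randomised are in the FAS, 152/4 = 38 per arm and 1/38 = 2.6 points.

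**Step 4: illustration.** Suppose, as an assumption, that the planned rates exclude responders on added therapy, and that a share r of non-responders in every arm becomes responders through it. Then p′ = p + r(1 − p), and each difference is multiplied by (1 − r).

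| r | 57% becomes | 50% becomes | 30% becomes | Top difference | Global power |
|---|---|---|---|---|---|
| 0 | 57.0% | 50.0% | 30.0% | 27.0 points | 80.1% |
| 0.02 | 57.86% | 51.0% | 31.4% | 27 × 0.98 = 26.5 | 78.4% |
| 0.05 | 59.15% | 52.5% | 33.5% | 27 × 0.95 = 25.65 | 75.8% |

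**Step 5: direction.** Add 1/35 to the response rate of the arms named, other inputs unchanged.

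| Added to | Top difference | Global power |
|---|---|---|
| Every arm | 27.0 points | 79.7% |
| Placebo only | 24.1 points | 70.9% |
| Each active arm only | 29.9 points | 87.1% |

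The documents do not say which pattern to expect. If the planned 57/57/50/30% already include such responders, the design loses no power relative to plan.

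**The case against.** **The rule is determinate.** A programmer would know what to do: score these patients as observed. That is a legitimate treatment-policy strategy. This stands, but neither document says it is intended. SAP 5.3 keeps patients in their randomised arm whatever treatment they received and says nothing about added UC therapy. NCF then treats the withdrawn patient the opposite way.

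**The per-protocol analysis deals with it.** Only partly. It may exclude these patients, but neither document defines a significant violation, and exclusion is not the same as counting as a failure. A reader might infer from SAP 3.3, which redefines the set to show results "based on observed results without non-completers considered failure (NCF) imputation", that the redefinition is why violators are not failed. It is not. That change concerns patients without Week 8 results. Significant violators are excluded under both the protocol and the SAP definitions, and neither definition fails them.

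**Stronger readings a reader might take.**
- That whether a patient fails rests wholly on the withdrawal decision. It does not, because a retained patient can still miss the response criteria.
- That one reclassified patient decides the trial. At 35 per arm, 19 active against 10 placebo responders gives p = 0.030, and 19 against 11 gives p = 0.055, past both the 0.0333 and 0.05 steps. But Hochberg also has a 0.10 step. With 19, 19 and 18 active responders against 11, the p-values are 0.055, 0.055 and 0.092, and all three doses are still declared.
- That the result is biased in a known direction. The documents give no basis for one.

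**Materiality is unproven.** This stands. The therapies are prohibited, use may be rare, and the 2% illustration costs 1.7 power points.

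**Conclusion.** The concern holds as a gap in the classification of the primary endpoint and the Week 8 binary secondary endpoints. The plan can count a response reached on prohibited or escalated UC therapy, and can score the same breach in opposite ways according to a discretionary withdrawal. It is not an error in any stated figure; the planned power reproduces.

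The only size that does not depend on assumed use is 2.9 points per patient at 35 per arm. The falls to 78.4% and 75.8% power assume equal conversion of non-responders in every arm and planning rates that exclude such responders. Real frequency and direction are unknown. The point is worth correcting because the remedy is cheap, not because harm has been shown.

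**What to change.** In SAP 15.1.1 and 15.2.2, with an entry in 3.3, state that a patient is a non-responder for the Week 8 binary endpoints if, between first dose and the Week 8 assessment, the patient:
- takes for UC a medication barred by protocol 6.6.2 or 6.6.3; or
- for UC, starts oral corticosteroids or oral 5-ASA/sulfasalazine, or increases them above the baseline dose.

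Permitted steroid reductions and courses given for other reasons do not count.

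Before the Week 8 unblinding in SAP 4.2, fix the medication list and a rule for partial dates and dose changes, and adjudicate blinded alongside the agreement of analysis sets in SAP 5. The date rule is needed because SAP Appendix 2 settles only prior versus concomitant status. It moves a partial start date to the earliest possible day, which can place a post-dose start before first dose. Keep the as-observed analysis as a sensitivity analysis in 15.1.2.

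If the unblinding has already happened (the documents do not date it), leave the primary analysis unchanged, state that it scores these patients as observed, and report the non-responder version in 15.1.2 as a post hoc sensitivity analysis.

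The cost is some extra SAP text and a little more blinded review. SAP 12 already provides for start and end dates, reason for use and daily dose. Response rates may fall slightly in any arm that has such responders. This is an analysis rule only and changes no patient's treatment.

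### The failure rule covers any missing Mayo subscore, so read literally it scores a fully observed 9-point responder as a failure when only PGA is blank

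*SAP*

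**What the plan says.** SAP 15.1 describes the Mayo score: "It consists of 4 subscores, each graded from 0 to 3 with higher scores indicating more severe disease". The list that follows is stool frequency, rectal bleeding, colonoscopy findings and PGA. The same section then says that the "9-point modified Mayo score is the Mayo score excluding PGA subscore", and defines primary response as a "decrease from baseline in 9-point modified Mayo score of at least 2 points and at least 30" percent, together with a rectal bleeding condition. PGA plays no part in that definition.

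SAP 15.1.1 imputes missing data by treating non-completers as failures (NCF) and adds a rule at subscore level: "If a patient is missing one or more Mayo subscores at the visit where the endpoint is being assessed", the patient is a failure. SAP 15.2.2 has the same rule for the dichotomized secondary endpoints: "if a patient is missing one or more Mayo subscores at the visit where the endpoint is being assessed", the result is again failure. Neither section limits the term to the subscores used by the endpoint in question.

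Protocol 9.3.4.2 and 9.3.4.3 give NCF for binary data and no subscore rule. SAP 3.3 (changes from protocol) does not list the added rule.

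**The concern.** NCF is meant for patients whose outcome is unknown. A patient with stool frequency, rectal bleeding and endoscopy all recorded at Week 8 has a known 9-point outcome, so nothing needs imputing. Taken at its word, the rule replaces that known outcome with a failure because a fourth item, outside the endpoint, is blank.

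The binary secondary endpoints show why one unqualified sentence cannot serve. Remission on the 9-point score needs three subscores, remission on the total Mayo score needs four, and endoscopic remission needs one. Under SAP 15.2.2 as worded, a patient with a qualifying endoscopic subscore fails endoscopic remission if a diary subscore or PGA is missing.

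Two things are at stake. Observed responders could be scored as failures, which lowers response rates and power. And the derivation of the primary endpoint is open to two readings, so a choice made after unblinding would be post hoc.

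**Working it through.** **Which subscores each endpoint needs, and what the rule checks**

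| Endpoint | Needed by its definition | Checked under a literal reading |
|---|---|---|
| 9-point response (primary) | stool, bleeding, endoscopy | all four |
| 9-point remission | stool, bleeding, endoscopy | all four |
| Total Mayo remission | all four | all four |
| Endoscopic remission | endoscopy | all four |

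Only for total Mayo remission do the two columns agree.

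**Inputs from SAP 3.1 and 15.1.1:** response rates 57% (8 mg QD), 57% (4 mg BD), 50% (4 mg QD) and 30% (placebo); 35 evaluable patients per arm; 152 randomized, which at the protocol's 1:1:1:1 ratio is 152/4 = 38 per arm; Hochberg at a two-sided familywise 0.10; stated global power 80%.

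**Reproducing the stated power.** Four binomial arms of n = 35 were simulated 400,000 times. Each dose was compared with placebo by the Mantel-Haenszel statistic in a single stratum (the documents give no stratum split), without continuity correction:

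z = d / √[p̄(1 − p̄)·2/n] × √[(2n − 1)/(2n)]

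Here d is the difference in observed rates and p̄ the pooled rate. Global success means largest p ≤ 0.10, or second-largest p ≤ 0.05, or smallest p ≤ 0.10/3 = 0.0333. Result: 80.1%, against the stated 80%. The simulation standard error is √(0.801 × 0.199/400,000) = 0.0006, or 0.06 points.

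**Effect of the literal rule.** Let m be the proportion of patients who have all three endpoint components but no PGA. The documents do not give m, so the values below are assumptions. If missingness is unrelated to arm and outcome, each observed rate becomes p(1 − m). The 57% v 30% difference becomes 27.0 × (1 − m) points. The expected number of responders scored as failures is 38 × (0.57 + 0.57 + 0.50 + 0.30) × m = 73.72 × m.

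| Assumed m | 57% v 30% difference (points) | Responders lost of 152 | Global power, n = 35 |
|---|---|---|---|
| 0 | 27.0 | 0 | 80.1% |
| 1% | 26.7 | 0.7 | 79.4% |
| 2% | 26.5 | 1.5 | 78.7% |
| 5% | 25.7 | 3.7 | 76.6% |
| 10% | 24.3 | 7.4 | 72.7% |

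One responder lost moves an arm by 1/38 = 2.6 points (1/35 = 2.9 points on the evaluable number).

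**Type I error.** With a 30% true rate in every arm, the simulated familywise error is 8.6%. If PGA were missing only on placebo, at 10%, it would be 9.9%, still within the 10% limit.

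**The case against.** The strongest reply is that the rule never names PGA and should be read as an explanation of NCF. SAP 3.3 supports this: it links NCF to patients without primary efficacy results at Week 8 and contrasts them with observed results. A patient with all three components is not a non-completer in the ordinary sense. That makes the narrower reading plausible as the authors' intent. But SAP 3.3 is explaining the per-protocol set, and it does not restrict the wording of 15.1.1 or 15.2.2.

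The trigger should also be uncommon. The Time and Event Table schedules the total, 9-point and partial Mayo scores at the same Week 8 visit, and protocol 7.2.4 lets missing diary days be replaced from the preceding 7 days. This stands, and it is why the effect is likely to be small.

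The sensitivity analysis in SAP 15.1.2 uses LOCF for the non-endoscopy subscores and BOCF for endoscopy. A patient missing only PGA would there be classified on the observed components, so the problem could show up as a gap between the two analyses. But that analysis is not the primary one, and it changes the handling of every other missing subscore too.

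Three stronger readings are tempting and are not supported:

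- A reader might infer that the rule brings the physician's subjective rating back into the endpoint. It would use only whether PGA was recorded, not its value.
- A reader might infer that the trial is materially underpowered. That needs 5% to 10% PGA-only missingness, for which the documents offer no basis.
- A reader might infer bias against the active arms. If PGA were missing only there, power would be 76.9%, 71.6% or 61.4% at 2%, 5% or 10%. Under the double-blind design, nothing in the documents points to such a pattern.

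**Conclusion.** The concern holds as a defect in a stated rule. SAP 15.1 makes PGA a Mayo subscore, and 15.1.1 and 15.2.2 fail a patient for any missing Mayo subscore. Followed literally, this overrides observed outcomes for the primary endpoint, 9-point remission and endoscopic remission. It cannot be said that responders will be lost, only that the text permits it and that the derivation could be programmed in two ways.

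The likely size is about 1 point of global power (80.1% to 78.7%) if 2% of patients lack only PGA. The 76.6% and 72.7% at 5% and 10% are illustrations. All of these figures assume missingness unrelated to arm and outcome, 35 patients per arm, the SAP's response rates and a single stratum. The change is worth making because it settles the primary derivation, not because a large loss is expected.

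**What to change.** Before unblinding, reword the rule in SAP 15.1.1 and 15.2.2 so that a patient is a failure when *missing one or more of the subscores that make up that endpoint*, and name them:

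- 9-point response and 9-point remission: stool frequency, rectal bleeding and endoscopy
- total Mayo remission: all four subscores
- endoscopic remission: endoscopy only

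Record the subscore rule in SAP 3.3, since the protocol has none. The cost is one clause in each of two sections, an entry in 3.3 and a small change to the derivation program. No new data, test or sample size is needed.
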